4.6.4. Multiple Comparisons

The analysis approaches described will likely involve a great number of individual statistical tests at both the univariate and multivariate levels. In some cases we utilize global statistical testing (e.g. omnibus contingency table assessments prior to marginal assessments). In other cases it will be appropriate to provide some protection against detecting false positive results by using a stepwise modeling procedure which enters and removes covariates based on

threshold values of p<0.15 and p<0.10 (or otherwise specified in the protocol), respectively, to initially reduce the number of candidate factors.¹¹¹ We are choosing to generally avoid severe adjustments of significance levels using multiple comparison techniques, which would lessen the chance of detecting potentially important biomarkers and other risk factors for severity of respiratory disease.¹¹² We take these more liberal approaches to dealing with multiple comparisons because PROP, an observational study, is considered a hypothesis generating rather than hypothesis testing study. Thus we will generally report significance values related to odds ratios for biomarker prediction of one year outcome as indicators for risk factors that are candidates for confirmation in future studies.

4.7. Specific Analytic Approaches

The specific analytic approaches to the assessment of which biomarkers play an important role in the prediction of one-year outcome will be discussed. The following sections provide a brief overview of some of the statistical methodologies and considerations that will be used at the time of analysis, both for descriptive purposes, and univariate and multivariate analyses relating biomarkers to one-year outcome(s). For a large study with many exposures or predictors, several outcome variables, and many scientific questions of interest, some of which will evolve with analysis itself, it is not possible to detail analyses of each question. Nonetheless, the types of analyses described here are likely to be used to answer many of the questions that arise. We consider here the principal methodological issues and approaches for dealing with those issues.

4.7.1. **Prediction of Outcome**

The primary focus of PROP is on the delineation of early biomarkers during the NICU hospitalization period that predict *respiratory morbidity through 1 year of age*. We have chosen to approach the assessment of this hypothesis using mixed effect logistic regression, Preliminary analyses will provide a parsimonious set of predictors to be considered in multivariate analyses. A full model will include all main effects (fixed) of parsimonious predictors and a random effect reflecting ICN variation and we will use variable selection techniques such as AIC, BIC and LASSO to select a subset of predictors as a candidate prediction model. All higher-order and interaction terms will be considered as well if there is any indication of effect modifier or non additive effects. For repeated measures, we will use generalized estimating equations (GEE¹¹³) for prediction of the outcome that can be implemented in SAS GENMOD procedure.

Center and Site Variability

The PROP is composed 6 designated clinical research centers (CRC), affiliated with 13 intensive care nurseries (ICN) and we will address both the CRC variation and the within CRC ICN variation. All testing models will be fitted separately for each CRC to see whether there are systematic differences among the five CRCs. Then, we can make explicit comparisons of one CRC to another by including the CRC differences as fixed effects in the regression model. For the second layer of variability, the within CRC ICN variability, we will treat the ICN effect as a "random" effect in the mixed effect linear or logistic models. This can be done because our

primary interest is in the effects of biomarkers across multiple ICNs and the number of ICNs is relatively large.

4.7.2. **ROC Analysis**

Biomarkers can be evaluated as diagnostic tests for both primary and secondary dichotomous outcomes. The sensitivity of the predictive function is defined as the proportion of participants with the primary outcome PRD, who have a positive test (e.g., duration of oxygen therapy); the specificity as the proportion of participants without the target condition who have a negative test. Multiple test cutoff points can be defined using different probabilities of the outcome derived from the logistic regression model. Each of these cutoffs is associated with a true positive rate and a false positive rate based on actual outcome. Optimal cutoffs can then be chosen based on their relative costs and benefits of the various types of errors.¹¹⁴ Analysis of an ROC curve, in which the sensitivity and (1-specificity) of the rule for different cutoff criteria are plotted¹¹⁵ will be used to graphically describe the relationship between chosen cutoff values of the logistic regression analysis and the associated test characteristics. The ability of the biomarker to discriminate between outcome groups will be reflected in the shape of this curve. The greater the integrated area beneath the curve, the greater the ability of the rule to differentiate individuals with/without the target condition.¹¹⁶ The ROC curve can be developed and tested using the algorithm of Hanley and McNeil¹¹⁶, adapted for use on a microcomputer by Centor and Schwartz.¹¹⁷

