Since the analysis will be adjusted for covariates including gender, birth weight, and gestational age at birth, the sensitivity of the analysis may be affected by the actual correlation between the biomarker and the covariate and the effect of the covariate. If multiple independent biomarkers can jointly explain the outcome, we are likely to have higher power to detect at least one of these biomarkers.

We may investigate the biomarker-outcome association analysis in a certain gestational age group. In the power assessment to follow, since the distribution of the numbers of infants born in 23-24, 25, 26, 27, and 28 weeks is close to uniform from sites' preliminary data, we assume there are 150 infants in each group, for which the power for detecting a significant association between biomarker and continuous outcome at $\alpha = 0.05$ is shown in Figure 4.4.3. Also in the same figure, we labeled the x-axis with the corresponding odds ratios assuming the power to detect the association between a biomarker and dichotomized outcome with an event rate of 40%. Given the subgroup sample size of 150, we will have 80% power to detect a significant association for an effect size of at least 0.24 (generally considered a small effect size) for a continuous outcome or an odds ratio of 1.64 or larger (a moderate OR) for a dichotomized outcome. Note that the minimum detectable effect size (Figure 4.4.3) required for subgroup analysis is more than twice that required using the full cohort (Figure 4.4.1, 4.4.2).

Figure 4.4.3: Power of detecting a significant association between a biomarker and the dichotomized/continuous outcome for various odds ratio/effect size (top/bottom x labels) in a subgroup at a significance level of α =0.05 assuming a missing rate of 10%.

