4.6.2. Multivariable Models

Multivariate models will be used to both simultaneously assess the contributions of the many biomarker predictors as well as to control for factors such as gender, race, products of multiple gestation, birth weight, gestational age at birth, site differences and between hospital variation, in the evaluation of potentially complex associations. Models specified in the protocol will include linear regression for continuous outcomes and logistic regression for binary or ordinal responses. We will provide in the analyses, in addition to tests of significance, confidence intervals for parameters of risk factors and biomarkers, and various approaches to assess the robustness of the estimates to nuisance factors. Particular attention will be paid to unusual observations (outliers) that may have undue influence on the analytical results. Standard regression diagnostics, including residual plots, and influence statistics will be used to identify such observations and examine their effect on analyses.

4.6.3. **Repeated Measurements**

For repeated measures, we will use generalized linear mixed models (GLMM¹⁰⁷) to account for dependence of the measures within subjects. We will first check for patterns in the residuals from the model without any random effect to determine plausible covariance structures that may account for the temporal correlation within subject¹⁰⁸ and then select the best one using routine likelihood-based criteria: maximized likelihood, largest Akaike information criteria (AIC¹⁰⁹), Schwarz information criterion (SBC¹¹⁰). We will use maximum likelihood method (ML) and residual maximum likelihood method (REML) for parameter estimates and significance testing.

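### Section 4.7.2 reads the ROC curve as the biomarker's discrimination without naming the predictors in the logistic model behind it; this is right only if the biomarker is the sole predictor

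*Protocol*

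**What the plan says.** Section 4.7.2 (ROC Analysis) opens with the marker as the thing being tested: "Biomarkers can be evaluated as diagnostic tests for both primary and secondary dichotomous outcomes". The curve is then built from a model: "Multiple test cutoff points can be defined using different probabilities of the outcome derived from the logistic regression model". Two sentences interpret it. One refers to the marker: "The ability of the biomarker to discriminate between outcome groups will be reflected in the shape of this curve". The next refers to something else: "The greater the integrated area beneath the curve, the greater the ability of the rule to differentiate individuals with/without the target condition". The section does not list the predictors in the model.

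Other sections describe logistic models with more than one predictor:

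- Section 4.7.1, immediately before: "A full model will include all main effects (fixed) of parsimonious predictors and a random effect reflecting ICN variation".
- Section 4.4.2: "Since the analysis will be adjusted for covariates including gender, birth weight, and gestational age at birth", in a remark about the sensitivity of the analysis.
- Section 4.6.2: multivariable models will "control for factors such as gender, race, products of multiple gestation, birth weight, gestational age at birth, site differences and between hospital variation".

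Section 4.6.1 also plans marginal, single-biomarker models as a screening step. The one stated benchmark for predictive ability is the set of existing BPD definitions (4.3.4). No model with the covariates but without the biomarker is named as a reference.

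**The concern.** An ROC curve drawn from a model's predicted probabilities describes everything in that model. If gestational age, birth weight and sex are in it, their discrimination is in the curve too. Section 2.3 says that respiratory risk falls as gestational age at birth rises, so a model containing gestational age can be expected to have an AUC above 0.5 before any biomarker is added. Calling that curve the biomarker's ability would credit the marker with what the covariates do.

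At stake is how well a reported marker appears to discriminate. Aim 1 concerns predictive accuracy relative to BPD diagnoses, and the study summary hopes for predictors that could serve as surrogate endpoints. A reader of the results would want to know what the marker adds to facts already known at birth.

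**Working it through.** **Inputs from the protocol.** N = 750 with 10% missing, so 750 × 0.9 = 675 analysed; PRD rate 40%; biomarker odds ratio 1.25 per SD, with 1.6 at the top of the range considered; two-sided α = 0.05 (all 4.4.1). Section 4.7.2 states no AUC, so there is no ROC figure to reproduce.

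**Check of the inputs against the plan's power statement.** For a standardised predictor, power = Φ(√(n·p(1−p))·ln OR − 1.96). Here √(675 × 0.4 × 0.6) = √162 = 12.73; 12.73 × ln 1.25 = 2.84; 2.84 − 1.96 = 0.88; Φ(0.88) = 81.1%. This agrees with the protocol's claim of more than 80%.

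**Case A: the model contains only the biomarker.** The predicted probability is then a monotone function of the marker, so the ranking and the ROC curve are the marker's own. In simulation (n = 675, PRD 40%) the two AUCs were 0.562 and 0.562 at OR 1.25, and 0.624 and 0.624 at OR 1.6. For a marker with no effect the fitted probabilities average about 0.52 against 0.50, because the fit chooses whichever direction happens to suit the sample. There is no inflation from covariates.

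**Case B: the model also contains gestational age (GA), birth weight and sex.** The marker is pure noise, independent of the covariates, and birth weight is correlated 0.7 with GA. The GA effect is an assumption, because the protocol gives none. 1,000 runs per row:

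| Assumed GA OR per SD | AUC, covariates + marker | AUC, covariates only | Difference | Marker's own AUC |
|---|---|---|---|---|
| 1.2 | 0.565 | 0.560 | 0.005 | 0.50 |
| 1.5 | 0.617 | 0.615 | 0.002 | 0.50 |
| 1.8 | 0.660 | 0.659 | 0.001 | 0.50 |

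These AUCs are computed on the data used for fitting. With cross-validation the gain over covariates is about zero.

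**Case B with a different scale for covariate strength.** Here the assumption is the SD of the joint covariate linear predictor. 300 runs per row:

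| Assumed SD | Noise marker: covariates + marker | Noise marker: covariates only | Marker OR 1.25: own AUC | Marker OR 1.25: covariates + marker | Marker OR 1.25: covariates only |
|---|---|---|---|---|---|
| 0.3 | 0.592 | 0.589 | 0.562 | 0.610 | 0.588 |
| 0.5 | 0.641 | 0.639 | 0.560 | 0.651 | 0.637 |
| 0.75 | 0.696 | 0.695 | 0.555 | 0.702 | 0.693 |
| 1.0 | 0.742 | 0.741 | 0.549 | 0.747 | 0.740 |

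At SD 0.5 the noise marker's adjusted-model AUC is 0.641 and that of a marker at OR 1.25 is 0.651, only 0.010 apart. Their own AUCs are 0.501 and 0.560. The marker at OR 1.25 adds 0.651 − 0.637 = 0.014 to the covariates. The shared covariate part therefore hides most of the difference between a marker with information and one without.

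**The case against.** The strongest reply is that section 4.7.2 never says its model contains covariates. It opens by treating biomarkers as diagnostic tests, its example of a positive test is a single measure (duration of oxygen therapy), and single-biomarker models are planned in 4.6.1. Under that reading the sentence is correct. The adjustment statements come from a power discussion and from the general multivariable section, and neither defines the ROC model. The section also assigns the area to the rule, which is the right label for a multivariable model. All of this stands, and it makes the point conditional.

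A reader might infer three stronger things, none of which the document supports:

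- **That a useless marker will be credited with the covariates' discrimination.** This follows only if the adjusted model generates the curve, which is not stated.
- **That useless markers will be declared significant by testing the AUC against 0.5.** Section 4.7.2 says that the curve can be developed and tested with a cited algorithm. It does not name 0.5 as the null value, and it does not make such a test the evidence for a single marker.
- **That the choice of candidate markers is undermined.** Selection uses univariate p-values or literature support (4.6.1), stepwise thresholds (4.6.4), and AIC, BIC and LASSO (4.7.1). The evidence to be reported for candidates is the significance of odds ratios (4.6.4), which are specific to the marker.

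It can also be said that 4.9 plans 10-fold cross-validation. That deals with optimism in the candidate final model, but it does not separate the marker's share from that of the covariates. Finally, the choice of ROC model might be left to an analysis plan. That would be a full answer if 4.7.2 were merely silent, but it states an interpretation that fails under the logistic model set out in the section just before it.

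**Conclusion.** The point holds in conditional form. Section 4.7.2 attributes one curve to two different things, the biomarker and the rule, and they coincide only for a single-marker model. If the adjusted model of 4.4.2, 4.6.2 and 4.7.1 is used, the statement about the biomarker is wrong: a marker with no information shows about 0.57 to 0.66 against its own 0.50, for an assumed GA odds ratio of 1.2 to 1.8 per SD. The direction follows from the protocol's own statement that risk depends on gestational age. The size cannot be derived from the protocol, and stronger assumed covariates give up to about 0.74. The simulations also assume a marker independent of the covariates. The harm is confined to the discrimination reported for a marker. It does not extend to which markers are chosen or to their odds ratios.

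**What to change.** In section 4.7.2:

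1. State that a biomarker's discrimination is shown by (a) the ROC curve of the biomarker alone and (b) the gain in cross-validated AUC of covariates plus biomarker over the same covariates without it, using the 10-fold scheme already planned in 4.9.
2. Label any curve drawn from the adjusted model as the discrimination of the whole model.

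The cost is about two sentences of text and one covariates-only reference model for each adjusted analysis. No further data are needed. The AUCs reported for biomarkers will be lower than those of the adjusted model, and gains over covariates may look small: about 0.01 to 0.02 for a marker at the protocol's OR of 1.25, in the simulations above.

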4.7.3. Missing Data

The optimal approach to missing data is assiduously avoiding it. It is likely that missing outcome data will be at or below an assumed 10% value, primarily because of mortality after 36 weeks PMA and some attrition. Nevertheless, extensive efforts will be made to collect complete one year data, with care taken to record participant primary and secondary participant contact telephone numbers and addresses, as well as reports of rehabilitation and nursing home visits, and follow-up for deaths, to death registries if necessary. If there is more than a trivial amount of missing outcome data, in secondary analyses, we will assess the impact of missing one year data. First, we will compare participants with substantially complete follow-up to those with missing one year data, with respect to observed baseline characteristics, and will pursue discrepancies to shed some light on the reasons for missing data in participants with incomplete follow-up. Second, we will investigate the impact of missingness on the estimates of effect levels and variability of effect estimates using multiple imputations.¹¹⁸

We will consider performing sensitivity analyses to assess the potential impact of missing data by fitting shared parameter models that relax the missing at random assumptions of the proposed random effects models. In addition, we shall also use inverse probability of censoring weighted methods of analysis to adjust for nonignorable dropout; when there are repeated measures of the outcome, this approach will be used in conjunction with generalized estimating equations to account for nonindependence of observations within participant.

4.8. Predictors of Specific Pulmonary Outcomes

The PROP investigators will attempt to perform RIP in all eligible infants at 36 weeks PMA. However, some infants will not be eligible, and others will not have recordings of sufficient quality. In considering sample size estimation below, we use one component of the composite dichotomized primary outcome, namely post-discharge rehospitalization.

4.8.1. Thoracoabdominal Asynchrony (Φ) as a Predictor of Post-discharge Hospitalization

We want to predict respiratory hospitalization using the phase angle Φ as measured during RIP testing. In order to estimate the sample size to achieve adequate power, we consider the hospitalization rate ranging from 30% to 50%. We also let the odds ratios (OR) for one standard deviation (SD) change in the Φ (1SD is about 40°)¹¹⁹ vary from 1.5 to 2.0 (both moderate effects). If we assume a conservative attrition rate of 10% (5% due to death and 5% due to loss to follow up), the total sample size required at the entry of the study in order to have 80% power to detect various odds ratios for hospitalization with a rate of 30-50% is shown in Figure 4.8.1. The required sample size decreases as either the hospitalization rate or the odds ratio to be detected increase. For example, to obtain 80% power to detect a significant association with OR of 1.5 (for one SD change of Φ) between Φ and hospitalization, we will require an initial sample size of 222, which after allowing for 5% post discharge mortality and 5% post discharge loss to follow-up will be an effective sample size of 200, at α = 0.05 using a two-tailed test when the hospitalization rate is 40%. We have chosen to attempt 253 evaluations of ϕ to be conservative (Table 4.8.1, hospitalization rate 30%, OR = 1.5).

Figure 4.8.1: Sample size required to obtain 80% power of detecting an association between Φ and respiratory hospitalization at a significance level of α = 0.05 (two tailed).

Table 4.8.1: Examples of sample sizes required to obtain 80% power of detecting a significant association between Φ and respiratory hospitalization

Hospitalization Rate	OR	Sample Size	
----------------------	----	-------------	--

30%	1.5	253
	1.7	248
40%	1.5	222
	1.7	130
50%	1.5	213
	1.7	124

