Rochester, Buffalo, St. Louis, and Cincinnati have already been qualified by the CF Foundation in performing research quality iPFTs. The remaining iPFT site (UCSF) can receive qualification by sending 10 deidentified iPFTs for review by the CF Foundation Therapeutics Development Network Infant PFT Core Center. During the study, data from RIP, oximetry, and iPFT will be sent to the CF Foundation Therapeutics Development Network Infant PFT Core Center where they will be over-read by two blinded, independent overreaders. Only data that are certified as research quality by both overreaders will be used for analysis. The Core Center has extensive experience with these procedures, having successfully used them in the CF Foundation infant PFT study¹⁰¹ and the preschool PFT study; the Core Center is also performing iPFT data management for the NIH/CFF funded Infant Study of Inhaled Saline. The physician director is [name]. The lab will work with the DCC to establish and test the data transfer protocol and then schedule routine data transfers. The iPFT Core Laboratory will participate in evaluating test data quality from clinical sites and advise the DCC regarding the need for intervention or retraining

4. Statistical Considerations

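### The 253 RIP evaluations in section 4.8.1 allow for death and loss but not for rejected recordings, so they are not conservative at a 30% hospitalization rate; separately, the 248 in Table 4.8.1 should be 148

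*Protocol*

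**What the plan says.** Section 4.8 of the protocol sets the scope of testing: "The PROP investigators will attempt to perform RIP in all eligible infants at 36 weeks PMA". The next sentence limits what this will yield: "However, some infants will not be eligible, and others will not have recordings of sufficient quality".

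Section 4.8.1 then gives a sample size for phase angle as a predictor of respiratory hospitalization. It uses 80% power, a two-sided 5% level, hospitalization rates of 30% to 50%, and odds ratios per standard deviation of 1.5 and upward. Attrition is 10%, made up of 5% death and 5% loss to follow-up. The worked example, at a 40% rate and odds ratio 1.5, is 222 at entry and 200 effective. The section ends with the planning decision: "We have chosen to attempt 253 evaluations of" phase angle, described as the cautious choice and tied to the 30%, odds ratio 1.5 cell of Table 4.8.1.

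Section 3.3.6, on RIP and iPFT data quality, sends RIP, oximetry and iPFT data to two independent overreaders and adds: "Only data that are certified as research quality by both overreaders will be used for analysis".

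Table 4.8.1 lists 253 and 248 at a 30% rate (odds ratios 1.5 and 1.7), 222 and 130 at 40%, and 213 and 124 at 50%.

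**The concern.** The 253 counts attempts, whereas power depends on infants who have both a certified recording and a known outcome. Two losses lie between these counts: rejected recordings, and death or loss to follow-up. The calculation covers only the second, although the protocol itself expects and enforces the first. The iPFT calculation in section 4.8.2 does allow for test failure, using a 75% success rate, so the omission for RIP is a difference between two neighbouring calculations.

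If 253 is taken literally as the number attempted, the stated 80% power does not hold in the cell the plan cites. It is also unclear how 253 attempts relates to testing all eligible infants in a cohort of 750 survivors.

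The 248 is a separate matter. Read as printed, raising the odds ratio from 1.5 to 1.7 at a 30% rate saves 5 infants (253 − 248), while the same change saves 92 at 40% (222 − 130) and 89 at 50% (213 − 124).

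**Working it through.** **Inputs, all from section 4.8.1:** two-sided α = 0.05 (z = 1.96); 80% power (z = 0.8416); hospitalization rate p of 30%, 40% or 50%; odds ratio (OR) per SD of 1.5 or 1.7; 10% attrition.

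**Step 1: reproduce the table.** For logistic regression on one standardised continuous covariate (Hsieh), the effective size is n = (1.96 + 0.8416)² / [p(1 − p)(ln OR)²], and the entry size is n / 0.9, rounded up. For p = 0.30 and OR 1.5, n = 7.849 / (0.21 × 0.1644) = 227.3, and 227.3 / 0.9 = 252.6, so 253.

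| Rate | OR | Effective n | n / 0.9 | Rounded up | Table 4.8.1 |
|---|---|---|---|---|---|
| 30% | 1.5 | 227.3 | 252.6 | 253 | 253 |
| 30% | 1.7 | 132.7 | 147.5 | **148** | **248** |
| 40% | 1.5 | 198.9 | 221.0 | 222 | 222 |
| 40% | 1.7 | 116.2 | 129.1 | 130 | 130 |
| 50% | 1.5 | 191.0 | 212.2 | 213 | 213 |
| 50% | 1.7 | 111.5 | 123.9 | 124 | 124 |

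Five of the six cells reproduce. Two conclusions follow: the 10% attrition factor is the only inflation in the 253, and 248 does not come from this method.

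**Step 2: test the 248 further.** Other attrition conventions (n / 0.95², n × 1.10) and the older Hsieh formula, with and without the attrition factor, give values from 146 to 186. None reaches 248. The table also shows the anomaly without any formula. The ratio of the OR 1.7 entry to the OR 1.5 entry is 130/222 = 0.59 at 40% and 124/213 = 0.58 at 50%, but 248/253 = 0.98 at 30%; with 148 it is 0.58. An entry size of 248 would give about 95% power at OR 1.7, where the table claims 80%.

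**Step 3: power of 253 attempts when a fraction f is unusable.** The analysed number is 253 × 0.9 × (1 − f), and power = Φ(√[n p(1 − p)] × ln OR − 1.96) with OR 1.5. The fractions f are assumptions, because the protocol gives no failure rate for RIP.

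| f | Analysed n | Power, 30% rate | Power, 40% rate | Power, 50% rate | Attempts for 80% at 30% rate |
|---|---|---|---|---|---|
| 0 | 227.7 | 80.06% | 85.0% | 86.4% | 253 |
| 5% | 216.3 | 78.0% | 83.2% | 84.7% | 266 |
| 10% | 204.9 | 75.8% | 81.2% | 82.7% | 281 |
| 15% | 193.5 | 73.4% | 78.9% | 80.5% | 298 |
| 20% | 182.2 | 70.8% | 76.5% | 78.1% | 316 |
| 25% | 170.8 | 68.0% | 73.8% | 75.5% | 337 |

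**Step 4: the rejection that 253 can absorb.** The tolerated fraction is 1 − (entry size required) / 253.
- 30% rate: 1 − 252.6/253, about 0.2%, which is less than one recording.
- 40% rate: 1 − 221.0/253, about 12.6%, or 31 recordings.
- 50% rate: 1 − 212.2/253, about 16.1%, or 40 recordings.

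**The case against.** The strongest defence is that the shortfall may never occur. RIP is planned in all eligible infants of a cohort of 750 survivors, and section 3.2 lets infants who could not be tested around 36 weeks be tested at 40 ± 1 weeks if still in hospital. Even 337 attempts would be 45% of 750 (337/750). Nothing in section 4.8.1 says that testing stops at 253, so the number can be read as a requirement for adequate power and not as a cap. This stands. It means that the two statements need to be linked; they do not exclude each other. A reader might infer that the phase angle analysis will be underpowered, and the documents do not support that.

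A reader might also infer that the plan's power collapses as soon as one recording is rejected. In the 30%, odds ratio 1.5 cell, one rejection does take power below 80%, but only from 80.06% to 79.9%, as would happen with any sample size rounded up to just meet its target. At the 40% rate of the protocol's worked example, 253 already contains a margin of about 31 recordings.

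It is also tempting to apply the 75% success rate from section 4.8.2. That rate belongs to iPFT, a sedated test at one year; section 3.2.2 presents RIP as less invasive and needing no sedation. The 25% row above marks one end of an assumed range and is not an estimate for RIP.

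On the 248, the defence is that nothing depends on it, which is correct. A digit misread in PDF text extraction cannot be fully excluded either, so the cell should be checked against the PDF before it is changed.

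Finally, the protocol describes PROP as hypothesis generating, and the 750 was fixed by the funding announcement. That limits the consequences but does not make the stated figures correct.

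**Conclusion.** The point holds in a limited form. The 253 attempted evaluations carry an allowance for death and loss to follow-up and none for rejected recordings, although the protocol foresees rejection and enforces it through double certification. In the cell from which 253 is taken there is no reserve: power is 75.8%, 70.8% or 68.0% if 10%, 20% or 25% of recordings are unusable. The description as conservative is justified with respect to the event rate at 40% or 50%, where 253 attempts keep at least 80% power up to about 12.6% and 16.1% unusable. It is not justified at 30%.

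These figures rest on the protocol's own inputs, on odds ratio 1.5, on 10% attrition, on rejection being independent of death and loss to follow-up, and on assumed unusable fractions. They also take 253 as the actual number of attempts, which testing of all eligible infants may well exceed.

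The 248 entry is wrong by the method that gives the rest of the table, which yields 148. A reader might infer that this undermines the planning target, but 253 comes from the odds ratio 1.5 row and does not change.

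**What to change.** 1. In sections 4.8 and 4.8.1, state that RIP is attempted in all eligible infants and that 253 is the number of recordings certified by both overreaders that is needed before death and loss to follow-up (253 × 0.9, about 228 analysed). Alternatively, keep 253 as attempts and restate its power over a range of assumed unusable fractions at 30%, 40% and 50% rates, as tabulated above. Either way, label the fractions as assumptions and do not carry the iPFT success rate over as the RIP rate.
2. In Table 4.8.1, correct the 30%, odds ratio 1.7 entry from 248 to 148 after checking the PDF.

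The cost is a text and table correction. Testing is already planned in all eligible infants, so enrolment, procedures and analysis do not change.
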